10.1 Vital Signs

Vital signs (blood pressure, heart rate, and body temperature) will be presented by time and treatment. Values at screening (visit 1), pre-administration (visit 5, day -1), post-administration (visit 5: 12, 24 and 48h post-administration), changes from pre-administration to 12, 24 and 48h post-administration, and at follow-up (visit 13) will be summarised for each variable by treatment.

Individual and mean values for the six measurements will be plotted for all variables.

Changes relative to normal ranges will be presented in shift tables with total number of subjects, and number and percent of subjects who experienced a shift from pre-administration (visit 5, day -1), to post-administration (visit 5: 12, 24 and 48h post-administration). The following categories are defined for these shift tables:

- Low: Values which are below the lower reference range limit;
- Normal: Values which are within the lower and upper reference range;
- High: Values which are above the upper reference range limit.

The reference limits for vital signs will be 90-180 mmHg for systolic blood pressure, 50-105 mmHg for diastolic blood pressure, 50-120 bpm for pulse, and <38.3°C for body temperature.

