### **9.7.3 Safety Assessments**

#### **9.7.3.1 Vital Signs**

Vital signs (blood pressure, heart rate, and body temperature) will be presented by time for each parameter and summarised by treatment. Shift tables will be presented for changes from baseline (i.e. the last assessment prior to administration) to the follow-up visit, and will be summarised by dose group.

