10.2 Clinical Chemistry, Haematology, and Urinalysis

Clinical chemistry, haematology and urinalysis parameters will be presented by time and treatment. Values at screening (visit 1), pre-administration (visit 5, day -1), post-administration (visit 5, day 3), the change from pre- to post-administration, and follow-up (visit 13) will be summarised for each laboratory variable by treatment.

Individual and mean values for the four measurements will be plotted for all numerical lab variables.

Changes relative to normal ranges will be presented in shift tables with total number of subjects, and number and percent of subjects who experienced a shift from pre-administration (visit 5, day -1), to post-administration (visit 5, day 3). The following categories are defined for these shift tables:

- Low: Values which are below the lower reference range limit;
- Normal: Values which are within the lower and upper reference range;
- High: Values which are above the upper reference range limit.
- Absent: No value for measured variable (for urinalysis)
- Present: Any value obtained for measured variable (for urinalysis)

The reference range limits will be the ones used by the analysing lab.

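### The vital-sign shift tables use limits too wide to show moderate rises, chiefly systolic, and stop at 48 h although the protocol specifies a shift to follow-up

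*SAP*

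**What the plan says.** SAP 10.1 describes the display this way: "Changes relative to normal ranges will be presented in shift tables with total number of subjects". Each value is classed Low, Normal or High, with High defined as "High: Values which are above the upper reference range limit". The limits are stated in one sentence: "The reference limits for vital signs will be 90-180 mmHg for systolic blood pressure, 50-105 mmHg for diastolic blood pressure", followed by "50-120 bpm for pulse, and <38.3°C for body temperature". No reason is given for these choices.

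The shifts run from pre-administration (Day -1) to 12, 24 and 48 h after dosing. The same section also summarises values at each visit and "changes from pre-administration to 12, 24 and 48h post-administration", and plots individual and mean values.

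For laboratory variables, SAP 10.2 uses the same Low/Normal/High layout with different limits: "The reference range limits will be the ones used by the analysing lab".

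Protocol 9.7.3.1 gives no numerical limits but does fix the time span: "Shift tables will be presented for changes from baseline (i.e. the last assessment prior to administration) to the follow-up visit". SAP sections 1 and 12 both state that the SAP introduces no changes to the analyses in the protocol.

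**The concern.** Safety and tolerability is one of the trial's two objectives, and vital signs are a named endpoint. The shift table is the only prespecified categorical summary of vital signs. Subjects are 21-40 years old and must be healthy on blood pressure at entry (protocol 4.1.1, a qualitative criterion), so they start far below 180/105 mmHg. A table headed as changes from normal, in which nearly every systolic entry reads Normal to Normal, invites reassurance that it cannot give.

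Two further defects sit in the same section. Low is a defined category, but temperature has no lower limit, so that category cannot be filled. And the table that the protocol asks for, baseline to follow-up, is missing without being declared as a change. The gap in time is material. The protocol expects a half-life of 40-44 h and counts adverse events as treatment emergent through Day 11, so a table ending at 48 h covers only the early part of that window.

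**Working it through.** The plan states no operating characteristic for these tables, so there is no figure to reproduce.

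**Inputs from the documents.** Limits: systolic 90-180, diastolic 50-105 mmHg, temperature below 38.3°C (SAP 10.1). Subjects: 24, in three groups of 8 (protocol 3.1.2). Half-life: 40-44 h (protocol 8.1.1).

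**Assumptions.** Neither document gives a blood-pressure distribution or a numerical eligibility limit. I take systolic mean 105-120 and SD 10-15 mmHg, diastolic mean 65-80 and SD 8-10 mmHg, normal distributions, independent women, and the same rise in everyone.

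**Step 1: rise needed to leave Normal upwards.** Rise = upper limit minus baseline.
- Systolic: from 100, 110, 120 or 130 mmHg, a rise of more than 80, 70, 60 or 50 mmHg.
- Diastolic: from 60, 70 or 80 mmHg, a rise of more than 45, 35 or 25 mmHg.

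A woman who goes from 110 to 175 mmHg systolic is tabulated Normal to Normal.

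**Step 2: chance that the table shows any High value.** For one reading, p = 1 - Φ((limit - mean - rise)/SD). For at least one of 24 women at one time point, P = 1 - (1 - p)^24.

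The systolic case most favourable to the plan at +20 mmHg has mean 120 and SD 15. Then z = (180 - 120 - 20)/15 = 2.67, p = 0.0038, and P = 1 - (0.9962)^24 ≈ 0.09. The least favourable has mean 105 and SD 10. Then z = 5.5, p = 1.9 × 10⁻⁸, and P is below 0.0001.

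| Uniform rise (mmHg) | P(any of 24 above 180 systolic) | P(any of 24 above 105 diastolic) |
|---|---|---|
| 0 | below 0.001 | below 0.001 to 0.14 |
| 10 | at most about 0.01 | 0.002 to 0.81 |
| 20 | below 0.0001 to 0.09 | 0.14 to above 0.99 |
| 30 | below 0.001 to 0.42 | 0.93 to above 0.99 |

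The systolic table is almost blind to rises up to about 20 mmHg across the whole assumed range. The diastolic table misses small rises in much of the range but registers large ones.

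**Step 3: contrast with narrower limits.** Purely for illustration, take 140/90 mmHg, which is not from the documents. At +20 mmHg, P becomes 0.81 to above 0.99 for systolic and above 0.99 for diastolic. The price shows at zero rise: P is then 0.006 (mean 105, SD 10) to 0.90 (mean 120, SD 15) for systolic, so benign High values would also appear.

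**Step 4: the lower systolic limit.** P(systolic below 90) runs from Φ((90 - 120)/10) = 0.0013 to Φ((90 - 105)/15) = 0.16. Among 24 women that is 0.03 to 3.8 expected Low readings per time point. The table need not be empty, but it is far more responsive at its lower end than at its upper end.

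**Step 5: time span, set side by side.** Protocol 9.7.3.1 requires baseline to follow-up (Visit 13, Day 11). SAP 10.1 gives pre-administration to 12, 24 and 48 h only. At 48 h, 48/44 = 1.1 to 48/40 = 1.2 half-lives have passed. At Visit 13, 10 days or 240 h after dosing, 240/44 = 5.5 to 240/40 = 6.0 have passed. The SAP summarises and plots follow-up values but has no shift table for that visit. This step needs no assumption.

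**The case against.** The strongest reply is that the shift table is one display among several. SAP 10.1 plots individual values, and with 8 women per group a rise to 175 mmHg would be plain to see. SAP 1.2.1 includes minimum and maximum in every continuous summary, so the largest change per group at 12, 24 and 48 h is tabulated. SAP 1.2.3 lists all subject data. Protocol 7.1.2.2 makes clinically significant vital-sign findings adverse events, whatever limits the SAP uses. All of this stands. A reader might infer that the safety analysis is blind to a blood-pressure rise, or that individual outliers would be lost in group means; the documents do not support either inference.

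A reader might also infer that the table cannot show an upward change at all. That goes too far: a value above 180 or 105 would be shown, a large diastolic rise probably would be, and a move from Low to Normal is itself an upward shift.

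It is also fair that the sizes rest on assumed baselines, that the trial is described as explorative with no decision rule on vital signs, and that SAP 10.2 is an imperfect model. A laboratory supplies its own ranges, whereas neither document defines site ranges for vital signs. The sponsor would have to specify them. The missing lower temperature limit is a small matter of definition with no bearing on blood pressure.

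None of this answers the point about the table itself. Plots give no counts, adverse-event capture depends on the investigator's judgement, and the wide limits carry the label normal without a reason. The missing follow-up shift is untouched by these arguments.

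**Conclusion.** The point holds for the categorical display only. With the SAP's limits the shift table is largely insensitive to moderate rises, most clearly systolic: the chance that any of 24 women is High at one time point after a uniform +20 mmHg is at most about 0.09 under the assumed mean of 105-120 and SD of 10-15 mmHg. At +30 mmHg it could reach 0.42 at the top of that range. Diastolic sensitivity depends strongly on the assumed baseline and is good for large rises. A table with few or no shifts to High should therefore not be read as evidence of no effect, but neither is a rise hidden from the rest of the plan. Temperature can never be Low as the limits are written.

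The second finding is separate and rests on the text alone: the SAP omits the baseline-to-follow-up shift table that protocol 9.7.3.1 specifies, while stating that no analysis was changed. It is the firmer of the two and should be corrected regardless of any view on the limits.

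**What to change.** 1. Add to SAP 10.1 the shift table from baseline to Visit 13 that protocol 9.7.3.1 specifies, or declare and explain its omission in SAP section 12.
2. For the shift tables, prespecify adult normal reference limits for each vital sign and state their source, or add a prespecified category of change from baseline. Keep the present limits as a separate count labelled markedly abnormal.
3. Give temperature a lower limit, or drop Low for that variable.

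The cost is SAP wording and one extra table, with no new data, visits or procedures, since vital signs are already recorded at Visit 13. The downside is that narrower limits will display more benign shifts, as the illustrative figures at zero rise show.

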10.2 Clinical Chemistry, Haematology, and Urinalysis

Clinical chemistry, haematology and urinalysis parameters will be presented by time and treatment. Values at screening (visit 1), pre-administration (visit 5, day -1), post-administration (visit 5, day 3), the change from pre- to post-administration, and follow-up (visit 13) will be summarised for each laboratory variable by treatment.

Individual and mean values for the four measurements will be plotted for all numerical lab variables.

Changes relative to normal ranges will be presented in shift tables with total number of subjects, and number and percent of subjects who experienced a shift from pre-administration (visit 5, day -1), to post-administration (visit 5, day 3). The following categories are defined for these shift tables:

- Low: Values which are below the lower reference range limit;
- Normal: Values which are within the lower and upper reference range;
- High: Values which are above the upper reference range limit.
- Absent: No value for measured variable (for urinalysis)
- Present: Any value obtained for measured variable (for urinalysis)

The reference range limits will be the ones used by the analysing lab.

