#### 7.1.2.4 Laboratory Parameters

##### Clinical chemistry, haematology, and urinalysis

Blood and urine samples will be collected at screening, on Day -1, Day 3, and at the follow-up visit for safety laboratory evaluations of clinical chemistry, haematology, and urinalysis parameters according to [Table 2](#). The clinical chemistry and haematology analyses will be performed at a local laboratory.

Urinalysis will be performed locally from a sample of mid-stream urine by means of a dip-stick test. In case any result of the dipstick is abnormal, a new urine test will be performed. If the abnormal result is confirmed, further examination may be initiated at the discretion of the investigator. Clinically significant abnormal findings will be reported as AEs.

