**Table 2 Safety laboratory parameters**

Clinical Chemistry	Haematology	Urinalysis
Alanine aminotransferase	Haematocrit	Protein
Albumin	Haemoglobin	Glucose
Alkaline phosphatase	Mean cellular volume (MCV)	Bilirubin
Aspartate aminotransferase	Mean corpuscular haemoglobin (MCH)	pH
Glucose	Mean corpuscular haemoglobin concentration (MCHC)	Nitrite
Calcium	Platelet count	Ketone
Chloride	Red blood cell count	Urobilinogen
Cholesterol	Reticulocytes	Blood
Creatinine	White blood cell count with differential count	Leukocytes
C-reactive protein	Neutrophils, eosinophils, basophils, lymphocytes	Specific gravity
Gamma-glutamyltransferase	Monocytes, large unclassified cells	
Phosphate		
Potassium		
Sodium		
Total bilirubin		
Triglycerides		
Urea (blood urea nitrogen)		

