#### **9.7.3.2 Clinical Chemistry, Haematology, and Urinalysis**

Clinical chemistry and haematology parameters will be presented as the vital signs parameters. Urinalysis parameters will be summarised by dose group and visit.

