9.1.1 Pharmacokinetic Endpoints

The calculation of PK parameters will be performed by Department of Translational Medicine, Ferring Pharmaceuticals. The PK parameters will be calculated for non-corrected as well as baseline corrected data by non-compartmental analysis (NCA) using the software Phoenix WinNonlin® (Certara, US). The baseline value is the mean of the three values obtained prior to the administration of the IMP (-1h, -30 min, 0 min). Baseline corrected values below LLQ will be set to zero. Actual sampling time points relative to dosing will be used for the NCA and on the individual plots of serum concentration versus time. Serum concentration values below lower limit of quantification (LLQ) and missing values (e.g. no blood sample collected or no value obtained at analysis) will be excluded from the estimation of λ_z . Values below LLQ will be represented as LLQ/2 in the plots and in descriptive statistics.

PK parameters will be estimated based on measurements from Day 1 to Day 10. From the serum concentration-time data of FE 999049 the following parameters will be estimated: AUC, AUC_t, % Extrap AUC, C_{max}, t_{max}, λ_z , t_{1/2}, CL/F, and V_z/F.

Selection of data points for calculation of t_{1/2} via λ_z will be based on the following considerations:

- The automatic range selection used in Phoenix WinNonlin® will be used to propose an optimal number of time points to use for the calculation of λ_z .
- The time range of samples used to estimate λ_z should preferably exceed the derived terminal half-life t_{1/2} ($= \ln 2/\lambda_z$).
- All the samples used to calculate λ_z should ideally fall in the log-linear terminal phase.
- At least three samples above LLQ obtained during the log-linear terminal phase will if possible be included in the calculation of the λ_z .

- The final selection of samples for calculation of λ_z will be based on visual inspection of log-concentration-time plots of individual profiles.

AUC will be calculated by the linear trapezoidal method. PK parameters will be summarised by treatment (i.e. dose group) using descriptive statistics.

Dose proportionality will be investigated for each of AUC and C_{max} using a multiplicative analysis of variance model (i.e. AUC and C_{max} will be log-transformed before analysis) with log(dose) as covariate. In this model, a covariate coefficient of 1 would indicate dose proportionality.

10 Safety

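### The urinalysis shift categories in SAP 10.2 turn on whether a value exists, not on whether the dipstick is negative or positive, so the table as written could not show a new positive finding

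*SAP*

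**What the plan says.** SAP Section 10.2 plans shift tables from pre-administration (Day -1) to post-administration (Day 3) for clinical chemistry, haematology and urinalysis. After the words "The following categories are defined for these shift tables" it lists Low, Normal and High, defined against the reference range, and then two categories marked for urinalysis:

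- "Absent: No value for measured variable (for urinalysis")
- "Present: Any value obtained for measured variable (for urinalysis")

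The list has no category for a missing result. It does not mention negative or trace results, and it does not say which urinalysis variables take Absent/Present and which take Low/Normal/High.

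The protocol describes the measurement in Section 7.1.2.4: "Urinalysis will be performed locally from a sample of mid-stream urine by means of a dip-stick test". Table 2 lists ten urinalysis parameters. For analysis, protocol Section 9.7.3.2 says only: "Urinalysis parameters will be summarised by dose group and visit". The Absent/Present rule is therefore a detail that the SAP adds, and the protocol holds no other version of it to fall back on.

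**The concern.** A urinalysis shift table is meant to show whether subjects who were negative before dosing became positive afterwards, for example for protein, glucose or blood. The two definitions do not separate negative from positive. They separate a result that was obtained from one that was not. A programmer who follows them exactly would put negative and positive subjects together under Present and keep Absent for subjects with no result.

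Laboratory parameters are a named safety endpoint in both documents. A table built this way would look reassuring because of how it was coded, and any shifts it did show would reflect sample availability. This is a rule that is stated and misclassifies, not one that is left out, so a programmer must either depart from the SAP or produce a table that says nothing useful.

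**Working it through.** There is no planned figure to reproduce. The check applies the two definitions as written to each possible dipstick outcome, and then looks for other text that would change the result.

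**Inputs**

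- The two category definitions and the Day -1 to Day 3 comparison: SAP 10.2.
- Dipstick testing: protocol 7.1.2.4. A tested pad gives a result, and a negative reading is taken here to be a result. The documents do not say how a negative is recorded, so this is an assumption, though it is the plain sense of any value being obtained.
- Parameters: protocol Table 2 lists protein, glucose, bilirubin, pH, nitrite, ketone, urobilinogen, blood, leukocytes and "Specific gravity", which makes 10. pH and specific gravity are numerical and can take Low/Normal/High. That leaves 10 − 2 = 8 for Absent/Present.
- Subjects: 24, with 8 in each of 3 dose groups.

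**Literal coding of each transition**

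| Day -1 | Day 3 | Coded as written | Coded by dipstick outcome |
|---|---|---|---|
| Negative | Negative | Present to Present | Absent to Absent |
| Negative | Positive | Present to Present | Absent to Present |
| Positive | Negative | Present to Present | Present to Absent |
| Positive | Positive | Present to Present | Present to Present |
| Negative or positive | No result | Present to Absent | Missing |
| No result | Negative or positive | Absent to Present | Missing |

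The first four rows fall into a single cell, so with complete data no clinical change of any kind can appear. The count is 24 subjects × 8 analytes = 192 subject-analyte pairs, all Present to Present whatever the dipsticks showed. The only way to leave that cell is to lack a result on one of the two days. A missing Day 3 sample could then look like resolution, and a missing Day -1 sample could look like a new finding.

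**Does other text correct this?**

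- SAP 9.1.1, on the pharmacokinetic data, speaks of "missing values (e.g. no blood sample collected or no value obtained at analysis"). That is nearly the wording used for Absent, and there it plainly means missing data. The same section names concentrations below the quantification limit separately from missing ones, so the SAP draws the needed distinction for serum FSH but not for urinalysis.
- SAP 10.4.2 says that missing values stay missing, with some exceptions, but that rule sits under adverse events and is written about adverse event attributes.
- Protocol 9.7.3.2 calls for a summary by dose group and visit and defines no categories.

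Nothing in either document redefines Absent or Present for urinalysis.

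**The case against.** The best defence is that Absent and Present are everyday terms for whether a dipstick analyte is detected. The list is introduced as showing changes relative to normal ranges. In that setting, value could mean a detected level, so that a negative pad has no value. This is probably what was intended, and an experienced programmer may well code it that way. It stands as a reason to treat this as a wording fault. It does not rescue the text: the SAP never mentions a negative result, its own pharmacokinetic section uses similar words for missing data, and even the kinder reading leaves trace results undecided and puts missing samples together with negatives.

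Three stronger readings are tempting, and the documents do not support them.

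- A reader might infer that all ten parameters are misclassified. Low/Normal/High appears in the same list, the section covers urinalysis, and the limits are those of the analysing laboratory. Nothing stops pH and specific gravity from using those categories. The SAP fails to allocate them, which is a gap, not an error in their coding.
- A reader might infer that abnormal urine findings would go unseen. SAP 10.2 also summarises urinalysis values at screening, Day -1, Day 3 and follow-up, SAP 1.2.3 lists all subject data, and the protocol makes clinically significant abnormal findings adverse events.
- A reader might infer that false shifts from missing samples would be common. The documents give no missing rate, and the Day 3 urine sample is collected before discharge from the residential stay.

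The retest is a separate matter. The protocol says "In case any result of the dipstick is abnormal, a new urine test will be performed", and neither document says which of the two results is analysed. One might infer that the repeat should replace the first. The protocol presents the retest as confirmation and does not give it that role. Because only abnormal results are retested, a replacement rule would alter abnormal results only. No recommendation on it is made here.

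**Conclusion.** The point holds as a fault in the written rule, and it is minor. As worded, the definitions code negative and positive results alike and treat a missing result as a finding. For 8 of the 10 urinalysis parameters, the shift table could not show a negative-to-positive change and could show a missing sample as a shift.

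This rests on two assumptions: that a negative dipstick reading counts as a value obtained, and that a subject with no result stays in the table. The SAP confirms neither in so many words. The second follows if the Absent category, as defined, is to be filled at all.

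The effect is limited to one descriptive safety table. The conclusion is not that the trial's urinalysis reporting as a whole would be wrong.

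**What to change.** Replace the two definitions in SAP 10.2 before programming starts:

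- Absent: the result is reported as negative.
- Present: any positive grade, with a statement of whether trace counts as positive.
- Missing: no result at Day -1 or Day 3, shown on its own line and left out of the shift denominator.
- Add that pH and specific gravity use the Low/Normal/High categories already in the list, and that the other eight parameters use Absent/Present.

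The cost is two or three lines of SAP text. No extra data, visits or samples are needed, and no other analysis changes.
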